The current project will test the efficacy of an Implicit Theory of Personality (ITP) intervention, which has provided excellent results in US both for depression and externalizing problems such as aggressive behavior. The project includes two studies, one focused on depression and another one focused on aggressive behavior. In addition, we will evaluate at which developmental stage the intervention is more effective. Finally, we will examine the moderation role of sex. The project includes biological data in a subsample of participants. Therefore, the project will contribute from a biopsychosocial and interdisciplinary perspective to the development of universal preventive interventions for depression and aggressive behavior, two important psychological problems in modern societies.

Preventive approaches to depression and aggressive behavior

Several depression prevention programs have been developed, such as the Coping with Stress program (Clarke et al., 1995), the Blues Program (Stice, Burton, Bearman, & Rohde, 2007), the UK Resilience Program (Challen, Machin, & Gillham, 2014), and the Penn Resiliency Program (Cardemil, Reivich, Beevers, Seligman, & James, 2006). Most prevention programs have targeted factors that have been found to increase risk for future onset of depression or increases in depressive symptoms, such as negative cognitions, social skill deficits, and ruminative style. The results from meta-analytic reviews of the effects of depression prevention programs for youth indicate that although results are good for indicated and selective preventive interventions, the average effects of universal preventive interventions on depressive symptoms from pretest to posttest are small (Mychailyszyn, Brodman, Read, &

Kendall, 2012; Stice, Shaw, Bohon, Marti, & Rohde, 2009). Interestingly, Stice et al. (2009) found that relatively shorter prevention programs produced significantly larger intervention effects than did longer prevention programs. Therefore, the authors concluded that long programs may not appeal to youth, which causes greater attrition and attenuated intervention effects. Thus, they recommended the use of brief interventions for future studies.

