Aim 2: To test whether the intervention changes biological and cognitive variables. From a biopsychosocial perspective, several mechanisms can explain the effect of the ITP intervention on psychological problems (depression and aggressive behavior). These mechanisms include changes in cognitive vulnerabilities and changes in the biological responses to the environmental stressors. If participants develop beliefs that personality traits are malleable, this should influence many maladaptive cognitive schemas. In fact, a feature of most maladaptive cognitive schemas is their absolute and stable nature (e.g., "I am a bad person", "The others will always reject me", "People hurt me on purpose", "I cannot put limits to my conduct". The intervention could also change biological indicators of stress (e.g., hormonal indicators). Therefore, in this project we will evaluate whether the ITP intervention affects cognitive vulnerabilities and biological indicators (cortisol, testosterone and DHEA in saliva).

Hypothesis: the association between the intervention and changes in psychological problems will be associated with changes in cognitive and hormonal variables. Some studies have explored whether the effects of interventions on depressive symptoms are mediated by changes in cognitive vulnerabilities with mixed results (Mychailyszyn et al., 2012). Thus, this project aims to contribute to clarifying mediational cognitive mechanisms.

Aim 3: To identify whether development and sex moderates the effects of the intervention. Regarding the developmental stage at which the preventive intervention is more effective, though studies are inconclusive, in general there is some consensus that cognitive vulnerabilities tend to consolidate in adolescence. Also in the case of

depression prevalence rates increase dramatically during adolescence. This supports the tentative hypothesis that the preventive intervention may be more effective if implemented early (i.e., before depression rates increase and cognitive vulnerabilities are consolidated).

As girls display higher rates of depression and boys higher rates of some modalities of aggressive behavior, sex could moderate the effects of the ITP intervention on psychological problems. For instance, we hypothesize that the ITP intervention will lead to a higher reduction of depressive symptoms in girls.

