Aim 4: To test whether temperament moderates the effect of the intervention. We hypothesize that the intervention will be more effective in adolescents high in neuroticism.

III. METHODS

This project will use a randomized controlled trial study design with pretest, posttest, six-month follow-up, and one-year follow-up. Group 1 (experimental group) will receive the ITP intervention and Group 2 (control group) will receive an educational intervention.

Study design and participants

We will conduct a double-blind randomized controlled trial (RCT) with two parallel groups in a large sample of volunteer adolescents (approximately n=900), from several high school centers (ages from 12 to 18 years). The schools will be randomly selected from the Basque Country. Participants will be randomly assigned to the experimental vs control groups. Group assignation will be done at the individual level within each classroom. Participants were randomized in a 1:1 ratio blocked by gender to one of two groups (experimental versus control condition). They were assigned to their allocated group in class by the researchers.

Measures

Depressive symptoms and aggressive behavior will be assessed by means of self-reports through the Center for Epidemiologic Studies Depression scale (CES-D; Radloff, 1977), the revised version of the Peer Experiences Questionnaire (RPEQ; Prinstein, Boergers, & Vernberg, 2001), the Cyber Bullying Questionnaire (CBQ; Calvete, Orue, Estévez, Villardón, & Padilla, 2010; Gámez-Guadix, Villa-George, & Calvete, 2014).

Measures of cortisol, DHEA and testosterone in saliva: A subset of the participants (around 50%) will provide saliva samples to be assayed for neuroendocrine levels to measure cortisol, DHEA and testosterone. Saliva samples will be collected at baseline (one week before the intervention), post-intervention (one week after the intervention) and at the two follow-ups (six-months and one-year follow-up). Data collection will occur in school and the time of assessments will remain

the same for each individual to minimize the effects of diurnal rhythms and reduce error variance. The adolescents will complete an intake survey (e.g., eating, drinking, exercise, and medication) that can potentially affect hormonal reactivity. The adolescents will then be directed to transfer saliva from their mouths to a tube. The sample tubes will be carefully labelled. As soon as the session ends, saliva samples will be sent to the assay laboratory.

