building on a long line of research on cognitive dissonance (Walton & Cohen, 2011). For a more complete description of the ITP intervention see Yeager et al. (2013). The intervention will be adapted to the developmental characteristics of the participants.

The **educational intervention** involves scientific information about the human brain. It was designed to be parallel to the experimental intervention and, hence, it has also three main parts. First, participants are asked to read scientific information about the different areas of the brain and their specialties. Second, participants read several testimonials written by upperclassmen about their transition to high school and how their brains help them to adapt to the new space and all the physical differences of the building and the classes. Finally, participants are asked to write a letter to another student explaining the main things he or she has learned about the brain and thinks are important for adapting to the new physical environment in high school. Hence it will control for the possibility that simple optimism about the potential for growth might account for our results. This is a conservative control group. An entity theory control group would be unethical in a longitudinal field experiment because it could teach the belief that personality cannot be changed, which has been associated to negative consequences.

Procedure

Parental informed consent forms will be sent to parents and adolescents. Those who accept to participate in the study will complete report measures at four waves: (1) one-week before intervention; (2) one-week after intervention; (3) six-months follow-up; and (3) one-year follow-up. Saliva samples will be collected at the same time points. Parents' participants will complete report measures at three waves: (1) one-week before intervention; (2) six-months follow-up; and (3) one-year follow-up. Intervention will be applied one week after the first survey. All the measures will be anonymous and participants will be asked to provide certain data (her/his birth date, first initial of mother's name, and first initial of father's name) to match their questionnaires, saliva samples and intervention tasks over time. Both interventions and assessment measures will be administered by research assistants during normal class time and last around 50 minutes.

Ethical considerations

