This study aims to develop and implement interventions that will be beneficial for the participating adolescents and other people in the future, by helping to increase their psychological wellbeing. Through randomization, the principle of justice will be respected, allowing all participants to have similar opportunities to receive the intervention. Gender will be considered and similar number of male and female participants will be included in the studies.

The risks are minimal and limited to answering psychological tests on stressors, psychological symptoms and cognitive styles. Previous experience with the same

questionnaires indicates that the risk is minimal. Adolescents can also decide to end their participation at any moment. Researchers collecting data will be trained to attend to any difficulty that could emerge while participants are responding to questionnaires. The researchers will give an alternative task (e.g., educational readings) to those participants who decide to end their participation.

Informed consent forms will be sent to parents or legal guardians to complete. Adolescents will also receive written information. The active consent of parents or legal guardians and of adolescents will be necessary for participation in the project. We will incentive adolescents for bringing parent forms, even when decision is negative.

Parents will be invited to complete measures of children's temperament and send their completed questionnaires in a stamped envelope that will be provided without any identifying information. Adolescents will complete the measures in the classroom. Saliva samples and their analysis will be processed according to existing regulations in a professional lab.

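### Does adapting the intervention to developmental stage, or losing school leavers at one year, undermine the Aim 3 test of moderation by age?

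*Combined protocol and SAP*

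**What the plan says.** The opening summary of the project says that "we will evaluate at which developmental stage the intervention is more effective". Section II, Aim 3, takes development and sex as moderators and offers, as a tentative hypothesis, that "the preventive intervention may be more effective if implemented early". Section III, Study design and participants, plans about 900 pupils aged 12 to 18 from several high schools, randomized 1:1 as individuals within classrooms.

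Section III, Preventive Intervention, describes the ITP session as one scientific reading, one collection of older pupils' statements and one writing task, refers to a published account for detail, and adds: "The intervention will be adapted to the developmental characteristics of the participants". On the control it says: "It was designed to be parallel to the experimental intervention and, hence, it has also three main parts". In the second of those parts, "participants read several testimonials written by upperclassmen about their transition to high school".

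On assessment, the Procedure section says: "Both interventions and assessment measures will be administered by research assistants during normal class time". Waves fall before and after the session, at six months and at one year, with saliva at the same points. Ethical considerations adds: "Adolescents will complete the measures in the classroom". Parents may return their forms by post. No such route is described for pupils.

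**The concern.** Two things look wrong at first.

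**Version and stage.** Over a six-year age range, adapting to development could mean different content for younger and older pupils. Version would then follow age, and an age-by-arm interaction could not separate how receptive pupils are at a given stage from how good their version was. Randomization within classrooms protects the comparison of arms at each age, not the comparison between ages. The control is called parallel, but the stated consequence is only its three-part structure. Its theme of moving to high school might also matter less to older pupils. At stake would be whether an Aim 3 result can be read as showing that earlier is better.

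**Leavers.** If the oldest pupils are in their last school year at entry, an in-class wave one year later would probably miss them. That removes the upper end of the age range, where a linear age interaction gets much of its information.

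**Working it through.** The plan gives no figure to reproduce: about 900 pupils are stated without power, effect size, SD or dropout. What follows illustrates size on assumed inputs.

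**Is either condition established?** The adaptation sentence is singular and follows a description of one set of materials. Section I describes the earlier single-session study as conducted in 9th graders, so one adaptation for a Spanish sample aged 12 to 18 is a natural reading. Nothing gives a number of versions or age cut-points. Likewise, the documents do not list the grades enrolled or say whether 12 to 18 is age at entry.

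**Size if versions differ.** Assume ages even over 12 to 18 (variance 6²/12 = 3.0), two versions split at 15, outcome SD 1, no baseline adjustment, no true stage effect, and a difference *d* between the versions' effects.

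- Older-versus-younger contrast: bias = *d*. With 225 pupils per cell, SE = √(4/225) = 0.133. Two-sided 5% rejection is 11.7% at *d* = 0.1 and 32.3% at *d* = 0.2.
- Linear age interaction: covariance of age and version = 0.5 × (16.5 − 15) = 0.75, so slope bias = 0.75/3 × *d* = 0.25*d* per year. SE = 2/√(900 × 3) = 0.0385. Rejection is about 10% at *d* = 0.1 and 25% at *d* = 0.2.
- One version: *d* = 0, rejection 5%.

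The first contrast is the less favourable, because its age cut sits exactly on the version split.

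**What would each possible change achieve?**

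- *Same age bands in both arms.* ITP version would still follow age, so *d* still enters in full. This only avoids a further mismatch in the control.
- *Recording the version.* If version is set by age, birth date, already collected for matching, largely determines it. Analysing age within version keeps 0.75/3.0 = 25% of the information, which doubles the SE.
- *One version for everyone.* This removes the aliasing, but reading level and relevance would then vary with age: a trade-off, not a clear gain.

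**Size of a loss of leavers at one year.** Information on the linear age interaction is proportional to the share retained times the variance of age.

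| Scenario | Share × variance | SE factor |
|---|---|---|
| No final-year pupils enrolled | 3.0 | 1.00 |
| All aged 17 or over lost (150 of 900) | 0.833 × 2.083 = 1.736 | √(3/1.736) = 1.31 |
| Half of those return a form | 2.425 | √(3/2.425) = 1.11 |

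With whole year groups instead of continuous age, losing the last of 5, 6 or 7 equal groups (180, 150 or 129 pupils) gives factors of 1.41, 1.32 and 1.26. For the overall arm contrast at an assumed effect of 0.2 SD, power falls from 0.85 with 900 pupils to 0.78 with 750.

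**The case for a change.** The strongest case for a change is that developmental stage is a named question, the documents do not settle whether content varies by age, and the Statistical Analyses Plan would not expose the problem: it lists families of methods without an interaction model, a definition of stage or a version variable. The steps proposed are cheap, and version is easier to record during delivery than to reconstruct afterwards.

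The conditional logic stands. If content followed age, a significant interaction could not be credited to stage alone, and a report should not do so. But Aim 3 asks whether the programme works better when given early. That is a question about timing, and a programme adapted to each stage can answer it. For that question the 10% to 32% are not false positives; they reflect a real difference between what younger and older pupils receive. Reading the aim as susceptibility with content held fixed is a choice the documents do not make.

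On leavers, a take-home or online form is the most concrete proposal, and on the figures above a half return would bring the factor from 1.31 to 1.11. Against that, it depends on final-year enrolment that is not confirmed, puts an unsupervised home mode beside classroom completion, and cannot recover the saliva due at the same wave. Because allocation is within classrooms, leaving should be about balanced between arms. The cost is precision and age range, not bias in the overall arm contrast. Depending on the month of enrolment, the six-month wave could be affected too.

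The remark that the transition theme matters less to older pupils is plausible, but nothing in the documents supports it.

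**Conclusion.** No change to the plan follows. Both points rest on conditions the documents do not establish, and the possible effect of each runs from nothing to moderate.

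Whether there is one version or several is missing detail that the team will know and can report. If there are several, the age comparison is valid for the age-adapted package, and the Aim 3 conclusion should be worded that way. That is ordinary care in reporting. None of the design alternatives is a clear gain: matched age bands leave the aliasing in place, a version record adds little to birth date, and a single version exchanges one age-related difference for another.

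If final-year pupils are enrolled and lost, the one-year age interaction is less precise (SE up by 31% if all aged 17 or over are missing, or by 26% to 41% when whole year groups are counted), and age conclusions extend only to the ages observed. The overall comparison of arms is not biased if leaving is balanced between them.

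All magnitudes assume even ages, a version split at 15, version differences of 0.1 to 0.2 SD, and complete loss of the oldest group except where a partial return is shown. None of these comes from the documents.

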Cognitive vulnerabilities: Two important cognitive vulnerabilities will be assessed: dysfunctional cognitive schemas and beliefs about implicit theories of personality. We will measure cognitive schemas that are relevant for depression (i.e., defectiveness, emotional privation) in the study about depression. We will use the Spanish version of the Young Schema Questionnaire (YSQ; Young, 2006). In addition, we will measure implicit theories of personality through the Implicit Theories of Personality questionnaire (Yeager et al., 2014).

Temperament traits: Temperament will be assessed by the revised version of the Early Adolescent Temperament Questionnaire (EATQ-R; Ellis & Rothbart, 2001) and the Big Five Questionnaire for children (BFQ-C; Barbaranelli, Caprara, Rabasca, & Pastorelli, 2003) for adolescents at the beginning of the study.

Parent reports: Parents will be invited to participate by responding measures about their children temperament by means of the revised version of the Early Adolescent Temperament Questionnaire (EATQ-R; Ellis & Rothbart, 2001) and the Big Five Questionnaire for children (BFQ-C; Barbaranelli et al., 2003) for parents and depressive symptoms through the CBCL 6/18 (Achenbach, 1991; Achenbach & Edelbrock, 1983). These data will be used in analyses in case that the response rate is enough.

Preventive Intervention

The **ITP intervention** lasts one session (of approximately one hour) and has three main parts: (1) scientific information; (2) normative stories from upperclassmen; and (3) self-persuasive writing exercise. In the first part, students read a scientific article that provides evidence that individuals have the potential to change. Participants read about actual neurological and behavioral studies showing that behaviors are controlled by “thoughts and feelings in brains,” and that pathways in the brain have the potential to be changed under the right circumstances. In the second part, participants read several normative quotes purportedly written by upperclassmen that previously read the same article and endorsed its conclusions. These quotes are obtained from previous interventions and edited by the team. These testimonials are provided to bring credibility to the incremental theory. Finally, in the last part, participants will be asked to write their own version of such a narrative to share with future students. This activity has been shown to facilitate the internalization of the intervention message,

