After completing measures, adolescents will be provided with information on services for adolescents (e.g., phone number of attention to adolescents). From an ethical perspective, the most important care aspect is the protection of information. We will follow the Directive 95/46/EC of the European Parliament, *Ley Orgánica 15/99 de 13 de diciembre de Protección de datos de Carácter Personal*, and of the Council of 24 October 1995 on the protection of individuals with regard to the processing of personal data and the free movement of such data. No identification data, such as names or surnames, will be used; instead, we will use a numeric code to match measures across times and sources (parents, and adolescents). Thus, each adolescent, and only he/she, will know his/her code. We will also follow the procedure for data protection that the University of Deusto has registered in the National Data Protection Agency. The project has been approved by the Ethics in Research committee of University of Deusto.

IV. STATISTICAL ANALYSES PLAN

Descriptive statistics of sociodemographic and study variables will be provided and several statistical strategies will be used to test the hypotheses. These will include mixed analyses of variance (ANOVA), multilevel analyses, regression analyses, among others. We will use IBM SPSS, MPLUS, LISREL, and HLM software for analyses.

References

Achenbach, T. M. (1991). Child Behavior Checklist/4-18 and 1991 profile. *Burlington, Vermont, USA: University of Vermont, Department of Psychiatry*.

Achenbach, T. M., & Edelbrock, C. S. (1983). Manual for the Child Behavior Checklist/4-18 and revised child behavior profile. *Burlington, Vermont, USA: University of Vermont, Department of Psychiatry*.

Blackwell, L. S., Trzesniewski, K. H., & Dweck, C. S. (2007). Implicit theories of intelligence predict achievement across an adolescent transition: A longitudinal study and an intervention. *Child Development*, 78(1), 246-263. doi:10.1111/j.1467-8624.2007.00995.x

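### Do two different descriptions of the record-linkage key put the link between arm and outcome at risk?

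*Combined protocol and SAP*

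**What the plan says.** The combined protocol and SAP describes record linkage in two places.

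- **III. Methods, Procedure.** "All the measures will be anonymous and participants will be asked to provide certain data": birth date and one initial for each parent. Their purpose is "to match their questionnaires, saliva samples and intervention tasks over time". Parent forms are not in that list. Of the parents, the same section says they "participants will complete report measures at three waves": baseline, six months and one year.
- **Ethical considerations.** No names are used. Instead, "we will use a numeric code to match measures across times and sources", with parents and adolescents named as the sources, and "each adolescent, and only he/she, will know his/her code". Parents return their forms in a "stamped envelope that will be provided without any identifying information".

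Three other statements bear on the point. Under Measures, parents report temperament and "depressive symptoms through the CBCL 6/18", to be analysed only if enough of them respond. Under Study design and participants, allocation is individual within classroom, blocked by gender, and carried out in class by the researchers. Ethical considerations also says: "The researchers will give an alternative task (e.g., educational readings) to those participants who decide to end their participation".

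**The concern.** Every aim needs each pupil's arm joined to baseline and follow-up, and the forms carry no names. Read closely, the text seems to leave three holes.

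1. **Co-twins.** They share a birth date and both parental initials, so the Procedure key is the same for both. Allocation is individual, so they can be in opposite arms. A swapped record would attach outcomes to the wrong arm.
2. **Parent forms.** A code known only to the adolescent cannot, taken literally, be written on a form that a parent posts in an unmarked envelope. An unlinked parent form has no arm and cannot enter an arm comparison.
3. **Pupils without a task.** The intervention tasks carry the key and differ by arm. They are the only arm-revealing records that the text says are matched. A pupil who left no task might have no documented route from allocated arm to outcome.

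Fields left off anonymous forms cannot be added later, which makes the point look worth raising before data collection.

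**Working it through.** The plan states no match rate or duplicate count, so there is no figure to reproduce. The check has two parts.

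**Are the two descriptions incompatible?** The Procedure gives the items that the pupil supplies. Ethical considerations summarises data protection. A code that the pupil generates from birth date and initials fits both. On that reading the statement that only the adolescent knows it is loose, since parents know the items too. It can be understood as saying that the team holds no list of names. The sentence before it says that parent records will be matched, so the step is intended. It is also feasible, because a parent can write the child's birth date and both initials on the form. The lack of identifying information most naturally describes the envelope, and it does not exclude a code on the form.

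**How large could the damage be?**

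From the documents: about 900 participants aged 12 to 18, allocated 1:1. Assumed, because the documents are silent: 0.5% to 3% of participants have an enrolled co-twin; 5 to 15 schools; probability H of 0.08 to 0.15 that two unrelated pupils share one parental initial.

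*Co-twins*
- Pairs: 900 × 0.005 / 2 = 2.25, to 900 × 0.03 / 2 = 13.5.
- About half in opposite arms: 1.1 to 6.8 pairs.
- If half of those were swapped unnoticed, with two pupils per pair, 1.1 to 6.8 pupils are misassigned, or 0.125% to 0.75% of 900.
- The effect shrinks by twice that share: 0.25% to 1.5%.
- If sex separates opposite-sex pairs (same-sex share assumed to be 1/2 to 2/3): 0.25% × 1/2 = 0.125%, to 1.5% × 2/3 = 1.0%.

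*Dropping all co-twins instead* (4.5 to 27 pupils). Detectable difference in SD units = 2 × (1.960 + 0.842) / √N, for two-sided 5% and 80% power, without clustering or covariate adjustment:
- N = 900: 5.604 / 30 = 0.187
- N = 895.5: 0.187
- N = 873: 5.604 / 29.55 = 0.190

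*Chance duplicates among unrelated pupils.* Expected pairs = S × C(900/S, 2) × H² / (365 × 6), where S is the number of schools whose records are matched separately:
- School not used (S = 1): 404,550 × 0.0064 / 2,190 = 1.2, to 404,550 × 0.0225 / 2,190 = 4.2.
- Matching within school: S = 15 gives 26,550 × 0.0064 / 2,190 = 0.08; S = 5 gives 80,550 × 0.0225 / 2,190 = 0.83.

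*Pupils with no task.* If 2%, 5% or 10% were lost (18, 45 or 90 pupils), N = 882, 855 or 810 and the detectable difference is 0.189, 0.192 or 0.197 SD.

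**The case for a change.** The strongest case for a change is asymmetry: one paragraph and a few extra fields cost little, while a missing field cannot be recovered. Three facts behind it stand. The two sections do describe the key differently. Co-twins cannot be told apart by birth date and initials, and sex does not separate same-sex twins. No sentence puts a key on the parent form.

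The harm drawn from those facts does not follow.

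- **Twins.** A duplicate key shows itself when records are matched, so silent swapping of half the opposite-arm pairs is a pessimistic case. Sex must be known for blocking and for the moderation analysis in Aim 3, and administration is by class. An analyst facing two identical keys would use both.
- **Parent forms.** At one parent per pupil and full response there would be 900 × 3 = 2,700 forms. That counts the forms that depend on the step, and none has been shown to be unlinkable. These data are secondary, since their use depends on response.
- **No task.** The alternative task is for pupils who end their participation, and the text around it concerns answering questionnaires. It says nothing about pupils who stay in follow-up without a task. The researchers delivered the allocation in class and so held it. Silence on how it was filed does not show that it was lost. An unfinished task that carries the key still shows the arm.

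Nor is the remedy free. Full birth date, parental initials, sex, school, class and a sibling item together come close to identifying a minor who is reporting depression and aggression. Ethical considerations treats protection of information as its foremost concern, and the anonymity and consent wording would have to change. A short key is a defensible choice.

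**Conclusion.** No change to the plan is needed. The difference between the two sections is loose wording about what can be a single self-generated code. The steps left unsaid (the parent copying the key, sex and class breaking ties, the arm being filed when it is allocated) are ones a competent team fills in.

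Under the assumed twin share of 0.5% to 3%, the worst case considered shrinks the effect by at most 1.5%. Excluding every co-twin raises the detectable difference from 0.187 to at most 0.190 SD. Chance duplicates number fewer than one pair if matching is within school. None of this would alter a conclusion about either outcome, and nothing in the documents points to linkage failing more often in one arm. The conclusion would be less secure if parent reports were a main outcome or if keys were matched without regard to school, sex or class. The plan indicates neither.
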